9.6 Immunogenicity Assessments

See [Section 9.5](#).

9.7 Genetics

Genetic assessments include deoxyribonucleic acid (DNA) and ribonucleic acid (RNA) analysis, as described in Section 9.8 (Biomarkers).

9.8 Biomarkers

Biomarkers are increasingly playing a key role in the development of cancer therapeutics. By evaluating treatment-induced changes in molecular markers measured in tissue and body fluids, the activity of experimental agents may be assessed and the details of their mechanisms of action may be elucidated. To explore potential predictive markers for clinical response to BMS-986207 in combination with nivolumab and ipilimumab, 4 types of specimens will be obtained from all participants for biomarker testing: (i) whole blood, (ii) serum, (iii) plasma, and (iv) tumor tissue. The sample subtypes and testing plans associated with each specimen type are described in the sections below and in [Table 9.8-1](#). Blood and tumor tissue samples will be collected in this study at baseline and on treatment to identify markers associated with clinical activity and mechanism of action of BMS-986207 in combination with nivolumab and ipilimumab. Complete instructions on the collection, processing, handling, and shipment of all samples described herein will be provided to sites in a separate Laboratory Manual.

Table 9.8-1: Biomarker Sampling Schedule

Study Day of Sample Collection ^a (1 Cycle = 6 weeks)	Tumor Biopsy ^b	Serum Biomarkers	Whole Blood PBMC	Whole Blood Immunophenotyping	Whole Blood DNA	Plasma for ctDNA
Screening	X	X	X			X
Cycle 1 Day 1		X	X	X	X	X
Cycle 1 Day 8		X	X	X		
Cycle 1 Day 15		X		X		
Cycle 1 Day 22		X		X		
Cycle 1 Day 29	X	X	X			
Cycle 2 Day 1		X	X	X		X
Every 4 cycles starting at Cycle 5 Day 1 until Cycle 17 (C5D1; C9D1; C13D1; C17D1)						X
Progression (optional) ^c	X	X	X			X
End of Treatment or Follow-up Visit 1						

Abbreviations: C, cycle; ctDNA, circulating tumor deoxyribonucleic acid; D, day; DNA, deoxyribonucleic acid; PBMC, peripheral blood mononuclear cells.

^a All collections in the table are mandatory except for collections at the time of progression, when they are optional, but strongly encouraged. All collections should be taken prior to the start of drug infusion. Detailed instructions for the collection, processing, and shipping of each sample will be provided in the Laboratory Manual.

^b Participant consent for archival biopsy or fresh biopsy collection at screening and fresh biopsy collection at C1D29 is mandatory, while it is optional at progression, but strongly encouraged. On-treatment tumor biopsy to be performed at C1D29 (\pm 5 days).

^c Unscheduled visit included to allow for biopsy and biomarker collection at progression.

9.8.1 Tumor Tissue Specimens

Consent for pre-treatment and on-treatment tumor biopsy samples is required for enrollment. Pre-treatment tumor samples are required from all participants, prior to randomization. A FFPE tumor tissue block (preferred, equivalent to 20 sections) or a minimum of 20 unstained slides of tumor tissue obtained during screening or prior to enrollment (within 3 months of enrollment and with no intervening systemic anti-cancer treatment between time of acquisition and enrollment) must be sent to the central laboratory prior to randomization. Samples may be from core biopsy, punch biopsy, excisional biopsy, or surgical specimen. Fine needle aspirates or other cytology samples are NOT acceptable. If despite best efforts, a minimum of 20 slides is not obtainable, submission of fewer slides may be acceptable in some circumstances following discussion with Sponsor or designee. Central laboratory must confirm receipt of evaluable tumor tissue as described in the Laboratory Manual prior to randomization. Assessment of tumor-cell PD-L1 expression by IHC also must be performed by central laboratory using pre-treatment tissue sample and results must be reported to IRT prior to randomization. Participants with inadequate sample are not eligible for treatment. Participants with indeterminate PD-L1 may be eligible if they have local PD-L1 results after discussion with Sponsor/Medical Monitor (or designee). On-treatment biopsies are mandatory if medically feasible on Cycle 1 Day 29. Detailed biopsy collection instructions will be available in the Laboratory Manual.

9.8.2 Biomarker Assessments in Tumor

Pre-treatment tumor samples will be assessed for PD-L1 expression using the Dako PD-L1 IHC 28-8 pharmDx validated assay. PD-L1 stained tissue sections will be assessed by a pathologist and membranous PD-L1 expression will be scored in tumor and immune cells per Laboratory Manual standard. Indeterminate PD-L1 tumor expression is defined as membrane staining that is obscured by high cytoplasmic staining or melanin content. Tumor tissue samples may be assessed by immunohistochemistry or other methods to determine the abundance of TILs and expression of immunoregulatory proteins by the tumor cell, TILs or surrounding stroma cells. Analytes may include, but are not limited to, TIGIT, DNAM-1, PVR, PD-L1, PD-1, CD8, and granzyme B (GzmB). Pharmacodynamic changes in TIL prevalence and the presence (and/or abundance) of immunoregulatory and other proteins may be examined. Baseline and pharmacodynamic measures may also be correlated to clinical outcomes. Sample analyses of messenger RNA (mRNA) may be completed using RNA isolated from tumor tissue. Targeted or whole transcriptome RNA sequencing, or similar methodologies may be used to assess gene expression signatures, such as, but not limited to, those associated with immune-related signaling, for potential association with clinical outcomes. DNA may also be isolated from the tumor tissue sample. Whole genome or whole exome sequencing may be performed using this DNA material to investigate potential associations between somatic mutations and copy number variation with efficacy measures. Tumor samples may be assessed for the expression of other immune related genes, RNAs and/or proteins, as well as the presence of immune cell populations using a variety of methodologies. Tumor tissue may also be used to investigate levels of TIGIT and BMS-986207 to assess receptor occupancy.

9.8.3 Biomarker Assessments in Peripheral Blood

Whole blood, serum and plasma samples will be collected at the times indicated in [Table 9.8-1](#) for the measurement of DNA, RNA, and protein biomarkers. A variety of biomarkers that may be associated with the treatment efficacy or pharmacodynamic activity will be investigated in peripheral blood specimens taken from all participants prior to and during treatment. These blood samples may be assessed for changes in quantity or phenotype of immune cell subsets, changes in soluble factors such as cytokines and chemokines, changes in immune cell functionality, changes in gene expression, circulating tumor DNA (ctDNA) and as germline control for TMB or determination of genetic changes within the tumor. These biomarkers may be used to assess pharmacodynamic changes and potential associations with efficacy. Additional biomarker assessments may also be performed if samples are available.

9.8.3.1 Exploratory Serum Biomarkers

Serum-based biomarkers are currently under investigation for their potential to predict or correlate with efficacy to immunotherapy. Serum samples may be assessed by enzyme-linked immunosorbent assay, seromics, ctDNA measurements, metabolomics, and/or other relevant multiplex-based protein assay methods for immune-related factors that may be associated with efficacy or AEs; such factors may include, but are not limited to, assessments of cytokines induced by IFN- γ signaling (eg, T-cell chemoattractants CXCL9 and CXCL10), chemokines, inflammatory factors, cytolytic markers (eg, granzyme A/B, perforin), ctDNA, and other soluble factors.

Additional or alternative methods for the profiling of serum markers may be based on the analysis of circulating anti-tumor antibodies. Furthermore, proteomic signatures of association with clinical response may be identified via proteome profiling of serum peptides at baseline and during treatment.

9.8.3.2 Whole Blood for Immunophenotyping

Flow cytometry will be used to assess baseline and serial on-treatment alterations in composition/activation status of immune-cell subsets present in the whole blood samples. Lymphocyte subsets to be assayed may include, but not be limited to, CD8+ and CD4+ T-cell subsets, central memory, effector memory cells, Treg cells and populations of those cells as defined by the expression of activation, exhaustion, or signaling markers, such as Ki67, cytolytic markers, and/or PD-1. Monocytes/macrophages and dendritic cell populations may also be monitored in a similar fashion, with a focus on characterizing subsets defined by the expression of lineage-specific markers.

9.8.3.3 Peripheral Blood Mononuclear Cells

Whole-blood samples will also be collected for isolation and cryopreservation of peripheral blood mononuclear cells (PBMCs). Blood samples may be used for immunophenotyping or characterization of the immune cell subsets in the circulation, including, but not limited to, T cells, B cells, NK cells, myeloid-derived suppressor cells, or subpopulations of the aforementioned immune cell types. These cryopreserved samples may be used for functional activation tests or for

additional assays if new biology suggests analysis beyond the immunophenotyping described above.

9.8.3.4 Whole Blood DNA

Whole blood collected from participants prior to study intervention initiation may be used to generate genomic DNA. Genomic DNA from whole blood may be used as a comparator for participants with tumors examined by whole-exome or genome-mutation analysis. Whole-exome or whole-genome sequencing methods may be used for this analysis.

9.8.3.5 Plasma for circulating tumor DNA

Circulating tumor DNA (ctDNA) is a valid surrogate tumor biomarker for monitoring tumor burden and responses to immunotherapies. Plasma ctDNA is more convenient to test, faster to obtain and less invasive, minimizing procedure-related risks and offering the opportunity to perform serial monitoring. Plasma samples will be collected at the time points indicated in [Table 9.8-1](#). Circulating tumor DNA (ctDNA) may be isolated from the plasma and may be assessed for association with TMB. Genomic profiles of ctDNA may be used to obtain information on tumor heterogeneity and to capture the emergence of resistant clones to therapy.

9.9 Additional Research

This protocol will include residual sample storage for additional research (AR).

For All sites:

AR is required for all study participants, except where prohibited by IRBs/ethics committees, prohibited by local laws or regulations, or academic/institutional requirements. Where one or more of these exceptions occurs, participation in the additional research should be encouraged but will not be a condition of overall study participation.

- If the IRB/ethics committees and site agree to the mandatory additional research retention and/or collection, then the study participant must agree to the mandatory additional research as a requirement for inclusion in the study.
- If optional participation is permitted and approved, then the study participants may opt out of the additional research retention and/or collection.

Additional research is intended to expand the R&D capability at Bristol-Myers Squibb, and will support as yet undefined research aims that will advance our understanding of disease and options for treatment. This may also include genetic/genomic exploration aimed at exploring disease pathways, progression and response to treatment etc.

Sample Collection and Storage

- Residual biomarker samples from peripheral blood and tumor tissue collections (see [Table 9.9-1](#)) will also be retained for additional research purposes

Samples kept for future research will be stored at the BMS Biorepository in New Jersey, USA or an independent, BMS-approved storage vendor.

The manager of these samples will ensure they are properly used throughout their usable life and will destroy the samples at the end of the scheduled storage period, no longer than fifteen (15) years after the end of the study or the maximum allowed by applicable law.

Transfers of samples by research sponsor to third parties will be subject to the recipient’s agreement to establish similar storage procedures.

Samples will be stored in a coded fashion, and no researcher will have access to the key. The key is securely held by the Investigator at the clinical site, so there is no direct ability for a researcher to connect a sample to a specific individual.

Further details of sample collection and processing will be provided to the site in the procedure manual.

Table 9.9-1: Residual Sample Retention for Additional Research Schedule

Sample Type	Timepoints for which residual samples will be retained
PK/IMG	All
Tumor Biopsy	All
Blood Biomarker Samples	All

Abbreviations: IMG, immunogenicity; PK, pharmacokinetic.

9.10 Other Assessments

Not applicable.

9.11 Health Economics or Medical Resource Utilization and Health Economics

Health economics/medical resource utilization and health economics parameters will not be evaluated in this study.

10 STATISTICAL CONSIDERATIONS

10.1 Statistical Hypotheses

It is expected that the PFS in participants with 1L Stage IV NSCLC and PD-L1 expression $\geq 1\%$ randomized to the BMS-986207 with nivolumab plus ipilimumab (Arm A) will be improved as compared to the PFS in participants receiving nivolumab plus ipilimumab (Arm B).

10.2 Sample Size Determination

The sample size of the study is calculated to have a sufficient probability of making the correct decision and have a low probability of making an incorrect decision under the pre-defined go criteria of primary efficacy endpoint of PFS in the PD-L1 $\geq 1\%$ subgroup. Using a Bayesian augmented control (BAC) design, a portion of the control cohort for Study CA020016 will be

borrowed from participants treated with nivolumab plus ipilimumab in Study CheckMate 227 whose baseline prognostic factors are similar to the current randomized population. Based on the results in the CheckMate 227 study, it is assumed that the median PFS in Arm B is 5 months with a constant HR of 0.605 of Arm A vs Arm B for the PD-L1 $\geq 1\%$ subgroup. The pre-defined go criteria at the end of the trial is probability (Pr) (HR < 1) > 0.9 and Pr (HR < 0.7) > 0.5. With the above assumption, 64 PFS events will need to be observed across the 2 arms, and there is 72.2% probability of making a go decision for a scenario at the interim analysis occurring at about 70% of the events, and 78.1% probability of making a go decision at the final analysis. This assumes 12 months for accrual and a minimum of 10 months follow up, for a total of 105 randomized participants with PD-L1 $\geq 1\%$ expression, with approximately 180 participants randomized under current assumptions of prevalence in the primary subgroup. The participants will be randomized to the BMS-986207 with nivolumab plus ipilimumab (Arm A) and the nivolumab plus ipilimumab (Arm B) in a 2:1 ratio.

The sample size of the study is planned to ensure a sufficient probability of making the correct decision and a low probability of making an incorrect decision under the pre-defined go criteria for the primary objective and is based on assumptions of expected prevalence of PD-L1 expression in the different PD-L1 subgroups. To ensure the randomized population is representative of the NSCLC population and to allow for appropriate subgroup analyses, total enrollment may be adjusted to ensure at least 105 randomized participants with tumor cell PD-L1 expression $\geq 1\%$, at least 75 randomized participants with tumor cell PD-L1 expression 1% - 49%, and at least 75 randomized participants with tumor cell PD-L1 expression < 1%, based on central laboratory results. The operating characteristics based on simulation under various scenarios are listed in Table 10.2-1 and Table 10.2-2. The simulation is conducted with FACTS 6.2 software (Berry Consultants, LLC).⁴⁰

Table 10.2-1: Operating Characteristics of Design Performance Under Different Sample Size, Borrowed Events, and Assumed True Hazard Ratios in the PD-L1 Expression $\geq 1\%$ Population

Historical Control		Current Control (mPFS)	Assumed True HR	N = 105 (2:1)		N = 90 (2:1)	
Historical Control (mPFS)	Borrowed Effective Events			Go%	No-go%	Go%	No-go%
			1	2.1%	90.0%	3.9%	88.4%
	14		0.7	49.1%	24.4%	51.9%	24.6%
5 months		5 months	0.6	79.3%	6.3%	77.9%	8.8%
			1	5.6%	84.4%	7.5%	81.9%
	1		0.7	49.0%	28.2%	50.8%	28.4%
			0.6	74.9%	10.7%	73.0%	13.1%

Abbreviations: HR, hazard ratio; mPFS, median progression-free survival; PD-L1, programmed death-ligand 1.

Table 10.2-2: Operating Characteristics of Design Performance Under Different Sample Size, Borrowed Events, and Assumed True Hazard Ratios in the All Randomized Population

Historical Control		Current Control (mPFS)	Assumed True HR	N = 180 (2:1)		N = 150 (2:1)	
Historical Control (mPFS)	Borrowed Effective Events			Go%	No-go%	Go%	No-go%
			1	0.3%	93.1%	0.6%	92.0%
	30		0.7	48.7%	11.1%	50.6%	15.7%
5 months		5 months	0.6	86.6%	1.4%	84.9%	2.2%
			1	1.6%	90.3%	2.8%	87.9%
	1		0.7	48.2%	21.4%	50.1%	23.9%
			0.6	80.4%	4.6%	79.5%	7.1%

Abbreviations: HR, hazard ratio; mPFS, median progression-free survival.

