Abbreviations: AxMP, auxiliary medicinal product; IP, Investigational Product; NA, not applicable.

Statistical Methods

Statistical Hypotheses

It is expected that the progression-free survival (PFS) in participants with 1L Stage IV NSCLC and PD-L1 expression $\geq 1\%$ randomized to the BMS-986207 with nivolumab plus ipilimumab (Arm A) will be improved as compared to the PFS in participants receiving nivolumab plus ipilimumab (Arm B).

Sample Size Determination

The sample size of the study is calculated to have a sufficient probability of making the correct decision and have a low probability of making an incorrect decision under the pre-defined go criteria of primary efficacy endpoint of PFS in the PD-L1 $\geq 1\%$ subgroup. Using a Bayesian augmented control (BAC) design, a portion of the control cohort for Study CA020016 will be borrowed from participants treated with nivolumab plus ipilimumab in Study CheckMate 227 whose baseline prognostic factors are similar to the current randomized population. Based on the results in the CheckMate 227 study, it is assumed that the median PFS in Arm B is 5 months with a constant hazard ratio (HR) of 0.605 of Arm A vs Arm B for the PD-L1 $\geq 1\%$ subgroup. The pre-defined go criteria at the end of the trial is probability (Pr) (HR < 1) > 0.9 and Pr (HR < 0.7) > 0.5. With the above assumption, 64 PFS events will need to be observed across the 2 arms, and there is 72.2% probability of making a go decision for a scenario at the interim analysis occurring at about 70% of the events, and 78.1% probability of making a go decision at the final analysis. This assumes 12 months for accrual and a minimum of 10 months follow up, for a total of 105 randomized participants with PD-L1 $\geq 1\%$ expression, with approximately 180 participants randomized under current assumptions of prevalence in the primary subgroup. The participants will be randomized to the BMS-986207 with nivolumab plus ipilimumab (Arm A) and the nivolumab plus ipilimumab (Arm B) in a 2:1 ratio.

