10.4.2 Primary Endpoint(s)

Table 10.4.2-1: Primary Endpoints

Primary Endpoint	Description	Timeframe
PFS by BICR in the PD-L1 $\geq 1\%$ population is defined as the time from randomization to the date of the first documented tumor progression by BICR or death from any cause.	The PFS curve will be estimated using the Kaplan-Meier product-limit method. A primary analysis will be based on the BAC study. A sensitivity analysis will be based on log-rank test stratified by the PD-L1 expression ($< 1\%$, $1\% - 49\%$, $\geq 50\%$) and histology will be used to compare PFS based on RECIST v1.1 by BICR between the 2 treatment arms. HR and corresponding 2-sided 95% CI for PFS primary endpoint analysis and 95% CI will be estimated using a Cox proportional hazard model, with treatment arm as a single covariate, stratified by above PD-L1 expression and histology to assist in interpretation of the PFS analysis.	Time from randomization and every 6 weeks after randomization for the first 48 weeks, then every 12 weeks, until progression (by BICR), death, study discontinuation or initiation of subsequent therapy

Abbreviations: BAC, Bayesian augmented control; BICR, blinded independent central review; CI, confidence interval; HR, hazard ratio; PD-L1, programmed death-ligand 1; PFS, progression-free survival; RECIST, Response Evaluation Criteria in Solid Tumors.

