10.5.1.1 Efficacy Interim Analysis

An interim analysis of PFS will also be done after approximately 70% of the total number of events are projected to have occurred. At this time, an interim analysis of ORR will also be done (anticipate approximately 126 participants will be randomized and followed for at least 2 post-baseline scans). The purpose of the interim analysis is for internal decisions outside the conduct of this trial. An independent statistician external to BMS will perform the analysis.

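### Section 10.2 pairs 64 PFS events with 12 + 10 months, but its assumptions give about 82 events by month 22 without dropout, and the stated N=105 go rates fit month 22

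*Combined protocol and SAP*

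**What the plan says.** Section 10.2 assumes a median PFS of 5 months in Arm B and a constant HR of 0.605 in the PD-L1 ≥ 1% population. A go decision requires Pr(HR < 1) > 0.9 and Pr(HR < 0.7) > 0.5. On this basis "64 PFS events will need to be observed across the 2 arms, and there is 72.2% probability of making a go decision" at an interim at about 70% of the events, and "78.1% probability of making a go decision at the final analysis". The calendar follows directly: "This assumes 12 months for accrual and a minimum of 10 months follow up, for a total of 105 randomized participants", allocated 2:1. The Protocol Summary repeats that "64 PFS events will need to be observed across the 2 arms".

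Table 10.2-1 gives go and no-go rates for N=105 and N=90, with 14 or 1 borrowed events. It does not say at what event count or calendar time they apply. Section 10.2 and Appendix 10 state no dropout rate.

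Section 10.5.1.1 times the interim by the event total: "An interim analysis of PFS will also be done after approximately 70% of the total number of events are projected to have occurred". It adds that "The purpose of the interim analysis is for internal decisions outside the conduct of this trial".

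**The concern.** The event total and the calendar sit in the same paragraph and are presented as one set of assumptions, so each should follow from the other. With a 5-month control median, most participants will have progressed or died well before 10 months, and 64 events among 105 participants looks low for that much follow-up.

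If 64 events triggers the final analysis, it comes about 6 months earlier than the calendar implies. The stated go and false-go rates and the 10-month minimum follow-up then do not describe it. If month 22 governs, 64 is not the expected event total, and the base of the 70% interim is unclear.

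**Working it through.** **Inputs.** From Section 10.2: control median 5 months, HR 0.605, 105 participants at 2:1 (70 in Arm A, 35 in Arm B), accrual 12 months, data cut at 12 + 10 = 22 months. From Appendix 10: a Normal prior on the log HR with mean 0 and SD 100 (effectively flat), and a Gamma(n, n/μ) prior on the control hazard. Assumed, because not stated: uniform accrual, no dropout (range shown), and historical hazard μ equal to the control hazard, as in the 5-month/5-month scenarios of Table 10.2-1.

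**1. Expected events at month 22.** Hazards per month are ln 2/5 = 0.1386 in Arm B and 0.605 × 0.1386 = 0.0839 in Arm A (median 8.26 months). For hazard h,

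P(event) = 1 − [exp(−10h) − exp(−22h)] / (12h)

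- Arm B: 1 − (0.250 − 0.047)/1.664 = 0.878; × 35 = 30.7
- Arm A: 1 − (0.432 − 0.158)/1.006 = 0.727; × 70 = 50.9
- Total: 81.7 events (SD 4.2), against 64 stated; 64/81.7 = 78%

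The exact chance of fewer than 64 events by month 22 is about 0.002%.

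**2. When 64 events are expected.** Replacing 10 and 22 by T − 12 and T gives 25.3 + 38.7 = 64 at T = 16.1 months, about 4 months after accrual ends.

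**3. Dropout.** With exponential dropout at rate d, replace h by h + d in the formula and multiply by h/(h + d). The last two columns use the model in step 4 with 14 borrowed events.

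| Annual dropout | Events at month 22 | Go, HR 0.605 | False-go, HR 1 |
|---|---|---|---|
| 0% | 82 | 78.4% | 2.2% |
| 10% | 78 | 77.8% | 2.3% |
| 20% | 73 | 77.5% | 2.6% |
| 30% | 69 | 77.0% | 2.8% |

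Reaching 64 at month 22 needs about 41% a year (about 4.5% a month), or about 29 of 105 participants censored before an event.

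**4. Which basis reproduces the stated go rates?** Under the Appendix 10 model the control hazard has posterior Gamma(n + events, n/μ + exposure). The Arm A hazard has posterior Gamma(events, exposure). Pr(HR < c) then follows from a Beta distribution. With 200,000 simulated trials per case at N=105, go % is:

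| Borrowed | True HR | Stated | Month 22 | 64 events |
|---|---|---|---|---|
| 14 | 1 | 2.1 | 2.2 | 3.6 |
| 14 | 0.7 | 49.1 | 50.3 | 49.3 |
| 14 | 0.6 | 79.3 | 79.6 | 76.6 |
| 1 | 1 | 5.6 | 5.0 | 7.9 |
| 1 | 0.7 | 49.0 | 50.0 | 49.3 |
| 1 | 0.6 | 74.9 | 75.4 | 72.6 |
| 14 (assumed) | 0.605 | 78.1 | 78.4 | 75.4 |

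The sponsor's run count is not stated. If it was 1,000, the six table cells give chi-square 1.9 on 6 df (p = 0.93) at month 22 and 20.2 (p = 0.003) at 64 events without dropout. The HR 0.7 cells do not separate the two. Nor do the N=90 cells: chi-square is 8.9 (p = 0.18) at month 22 and 5.8 (p = 0.45) at 64 events.

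Table 10.2-2 (N=180) also fits month 22. Stated against simulated go is 0.3/0.3 and 86.6/86.7 with 30 borrowed events (HR 1 and 0.6), and 1.6/1.7 and 80.4/81.4 with 1.

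**5. Interim.** Seventy percent of 64 is 45 events (about month 12) and 70% of 82 is 57 (about month 14.5). Simulated go with 14 borrowed events is 72.6% and 74.4%, against 72.2% stated. That is closer to 45, but a gap of about 2 points is not conclusive.

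**The case against.** The strongest defence is that both numbers could be true together. In Table 10.4.2-1 PFS assessment runs "until progression (by BICR), death, study discontinuation or initiation of subsequent therapy", treatment decisions follow the investigator while events are counted by BICR, and the resulting censoring could bring month 22 down to 64 events. On the 1,000-run assumption, 4.5% dropout a month gives chi-square about 9.9 on 6 df (p about 0.13) for the six N=105 cells, so it is not formally excluded. It fits worse than no dropout, however: about 76.7% go at HR 0.605, and false-go of 3.2% and 7.0% with 14 and 1 borrowed events. Table 10.2-2 also favours no dropout (chi-square about 2.6 against 12.7). A loss of about 29 of 105 participants would have to be a stated design assumption.

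A second defence reads 64 as a floor. If every participant had exactly 10 months, 70 × 0.568 + 35 × 0.750 = 66 events would be expected, close to 64. But that is not staggered entry over 12 months with 10 months as the minimum. A floor that is missed about 0.002% of the time never binds. On this reading the final probabilities do stand, and only the event figure is wrong.

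It is also fair that the size is modest and that run count, accrual shape and the borrowing behind 78.1% are unstated; with 1 borrowed event, month 22 gives 74.4%. The later SAP may name a trigger, but that would not reconcile the figures in Section 10.2. On the interim, Section 10.5.1.1 also expects about 126 randomized participants with at least 2 post-baseline scans. At uniform accrual of 180 over 12 months that is 126/180 × 12 = 8.4 months plus 12 weeks, or about month 11, nearer 45 events than 57. The interim serves internal decisions only, so little turns on it.

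**Conclusion.** The concern holds. On the stated assumptions, with uniform accrual and no dropout, 12 + 10 months yields about 82 PFS events rather than 64, and 64 falls about 6 months earlier. The final go and false-go figures for N=105 match month 22. This rests on the HR 1 and HR 0.6 cells, and on 78.1% if 14 events are borrowed. Analysing at 64 events would cost about 3 points of go (78.4% to 75.4%) and add about 1.4 points of false-go (2.2% to 3.6%). Minimum follow-up would fall from 10 to about 4 months.

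The event shortfall is firm unless heavy censoring was assumed and left unstated. The attribution of the go rates to month 22 is well supported but depends on the assumed run count and borrowing. The interim inference is suggestive only.

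**What to change.** In Section 10.2 and the Protocol Summary, state whether an event count or calendar time triggers the final analysis. State also the dropout or censoring assumption and the number of borrowed events behind 72.2% and 78.1%. Then re-run the sponsor's simulation so that the event total, follow-up, interim fraction, and go and false-go rates share one basis. There are two consistent options:

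- **Keep month 22.** Replace 64 by the expected events under the stated dropout (about 82 only if there is none; 78 to 69 at 10% to 30% a year), and set the interim at 70% of that total.
- **Keep 64 events.** Restate the final go probability (about 75% here), false-go (about 3.6% here) and minimum follow-up (about 4 months at HR 0.605). The published figures should come from the sponsor's re-run.

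The cost is wording in two places and one simulation re-run. No patients are added, and the endpoint, model and go rule do not change. Under the second option the stated characteristics become slightly less favourable.
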